### **6.2.1. Preparation and Dispensing**

See the IP manual for instructions on how to prepare the study intervention for administration. Study intervention should be prepared and dispensed by an appropriately qualified and experienced member of the study staff (eg, physician, nurse, physician's assistant, nurse practitioner, pharmacy assistant/technician, or pharmacist) as allowed by local, state, and institutional guidance. A second staff member will verify the dispensing.

Only qualified personnel who are familiar with procedures that minimize undue exposure to themselves and to the environment should undertake the preparation, handling, and safe disposal of biotherapy agents.

## **6.3. Measures to Minimize Bias: Randomization and Blinding**

### **6.3.1. Allocation to Study Intervention**

This is an open-label study. No randomization or blinding mechanisms will be used; however, the specific study intervention dispensed to the participant will be assigned using an IRT.

The site personnel (study coordinator or specified designee) will be required to enter or select information including but not limited to the user's ID and password, the protocol number, and the participant number. The site personnel will then be provided with a treatment assignment, and DU or container number when study intervention is being supplied via the IRT system. The IRT system will provide a confirmation report containing the participant number, and DU or container number assigned. The confirmation report must be stored in the site's files.

The study will start with enrolling 30 participants in Part 1. Part 2 enrollment will start based on a joint agreement between the sponsor and the investigators after the review of the available data, including CRS incidence and severity.

Allocation to dose level will be decided by the sponsor based on the participant's eligibility and availability of open slots. Study intervention and allocation of participants will be assigned using IRT. The investigator's knowledge of the treatment should not influence the decision to enroll a particular participant or affect the order in which participants are enrolled.

Following full assessment and determination that the participant meets all eligibility criteria, the investigator or designee will enroll the participant.

For Part 2A and Part 2C, no participant shall sign the informed consent document until the investigator or designee has received the confirmation of the participant's screening in writing from the sponsor or delegate.

Study intervention will be dispensed at the study visits summarized in the [SoA](#). The study-specific IRT reference manual and IP manual will provide the contact information and further details on the use of the IRT system.

#### **6.4. Study Intervention Compliance**

Participants are dosed at the site, they will receive study intervention directly from the investigator or designee, under medical supervision. The date and time of each dose administered in the clinic will be recorded in the source documents and recorded in the CRF. The dose of study intervention and study participant identification will be confirmed at the time of dosing by a member of the study site staff other than the person administering the study intervention.

The site will complete the required dosage Preparation Record located in the IP manual. The use of the Preparation Record is preferred, but it does not preclude the use of an existing appropriate clinical site documentation system. The existing clinical site's documentation system should capture all pertinent/required information on the preparation and administration of the dose. This may be used in place of the Preparation Record after approval from the sponsor and/or designee.

Compliance with study intervention will be documented in the source documents and CRF. Study intervention start dates, reasons for delays, dose reductions, and/or missed doses will be recorded in the CRF. Deviation(s) from the prescribed dosage regimen will be recorded in the CRF.

A record of study intervention dispensed and administered to each participant must be maintained.

## 6.5. Dose Modification

Every effort should be made to administer study intervention on the planned dose and schedule.

The recommended dose modification guidelines for participants who have active confirmed (positive by regulatory authority-approved test) or presumed (test pending/clinical suspicion) SARS-CoV-2 infection can be found in [Appendix 8](#).

In the event of significant toxicity, dosing may be modified in any cycle as described in [Table 6](#). All dose modifications should be based on the worst preceding toxicity and must be recorded on the CRF.

### 6.5.1. Elranatamab

#### 6.5.1.1. Redosing Criteria

**During a Cycle:** Re-treatment following interruption for treatment-related toxicity and for peripheral neuropathy (any causality) within a cycle should follow the dose modification tables and guidance below.

**At the Start of a Cycle:** Dosing at the start of any new cycle should not occur until all of the following parameters have been met:

- $ANC \geq 1.0 \times 10^9/L$
- Platelets count  $\geq 25 \times 10^9/L$
- Recovery of treatment-related non-hematologic toxicities to baseline or Grade  $\leq 1$  severity
- For any dosing day (at start of a cycle or during a cycle), no ongoing CRS or ICANS of any grade
- Recovery of treatment-emergent peripheral neuropathy to Grade  $\leq 1$  severity
- Recovery of any lung infection or other serious infection to baseline

#### 6.5.1.2. Dose Modifications for Elranatamab-Related Toxicity and for Peripheral Neuropathy

The dose modifications for elranatamab-related toxicities and for peripheral neuropathy (any causality) are presented in [Table 6](#). All dose modifications should be based on the worst preceding toxicity and must be recorded on the CRF.

**Table 6. Dose Modifications for Elranatamab-Related Toxicity and for Peripheral Sensory or Motor Neuropathy**

Toxicity	Grade 1	Grade 2	Grade 3	Grade 4
Non-hematologic (excluding peripheral neuropathy – see below)	Continue treatment. a	Continue treatment. Alternatively, per investigator discretion, withhold treatment until toxicity is Grade ≤1, then resume. a	Withhold treatment until toxicity is Grade ≤1 or has returned to baseline, then resume treatment. a,b	Permanently discontinue. a,b
Hematologicc,d	Continue treatment.	Continue treatment.	Withhold treatment until toxicity is Grade ≤2 or has returned to baseline, then resume treatment. d	Withhold treatment until toxicity is Grade ≤2 or returns to baseline. d
Peripheral sensory or motor neuropathy (any causality) See Section 8.3.8 for recommended work-up.	Continue treatment.  Continue to monitor the participant for signs of worsening neuropathy. e	For new or worsening Grade 2 peripheral neuropathy withhold treatment until resolution to Grade ≤1, then resume treatment.  Continue to monitor the participant for signs of worsening neuropathy. e  If Grade ≥2 neuropathy reoccurs, permanently discontinue elranatamab.	First occurrence: withhold treatment until neurologic toxicity symptoms improve to Grade ≤1.  Recurrent: permanently discontinue elranatamab.	Permanently discontinue elranatamab

a Both elranatamab priming doses must be administered before the full elranatamab dose. If C1D4 dose cannot be administered on the planned date, elranatamab treatment may restart at the planned 20 mg C1D4 dose upon meeting the re-treatment criteria. If the 20 mg dose is tolerable, elranatamab should then be increased to the full 76 mg dose 1 week later. If after C1D4, a participant experiences a treatment-related adverse event that leads to a dose interruption or delay (ie, dose held on C1D8), elranatamab treatment may restart at the same dose (20 mg) upon meeting the re-treatment criteria (Section 6.5.1). If the 20 mg dose was tolerable, the elranatamab dose should be increased to 76 mg. In case of ongoing CRS or ICANS of any grade on any dosing day, dosing will be held until CRS or ICANS resolution.

b Grade 3 or 4 nausea, vomiting or diarrhea must persist at Grade 3 or 4 despite maximal medical therapy to require dose modification or permanent discontinuation.

c Excludes lymphopenia which is expected based on the elranatamab mechanism of action.

d For thrombocytopenia: dosing can continue if platelets  $\geq 25 \times 10^9/L$ .

e Consider additional diagnostic work-up (see Section 8.3.8).

**Note:** Cycles will not be extended to allow make-up for missed doses.

Doses may be held as needed until toxicity resolution. Appropriate follow-up assessments should be done until adequate recovery occurs as assessed by the investigator.

Missed doses will not be made up and cycles will not be extended to allow for missed doses.

C1D1 will be based on Day 1 of elranatamab dosing. After C1D1,

- for QW regimen, if elranatamab cannot be administered on the planned day including the protocol defined window ( $\pm 3$  days), it should be skipped until the next planned dose (ie, if Day 15 cannot be administered within  $\pm 3$  days of planned dose, the dose should be skipped until Day 22).
- for Q2W regimen, if elranatamab cannot be administered on the planned day including the protocol defined window ( $\pm 3$  days), it should be skipped until the next planned dose (ie, if Day 15 cannot be administered within  $\pm 3$  days of planned dose, the dose should be skipped until Day 1 of the next cycle).
- For Q4W **CCI**, if elranatamab cannot be administered on the planned day including the protocol defined window ( $\pm 6$  days), it should be skipped until Day 1 of the next cycle.

Participants must receive both elranatamab priming doses before receiving the elranatamab 76 mg dose. If C1D4 cannot be administered within the protocol defined window, elranatamab treatment may restart at the planned C1D4 dose upon meeting the re-treatment criteria. Upon re-treatment, if the C1D4 dose was tolerable, the elranatamab dose should be increased to the 76 mg dose 1 week later, after which QW dosing with the 76 mg dose should continue. If elranatamab treatment is interrupted for  $>2$  weeks within the first cycle between the 20 mg priming dose and the first full dose (76 mg), the participant should be retreated with 20 mg elranatamab. If well-tolerated, the elranatamab dose can be escalated to 76 mg 1 week later.

For Part 2, participants should receive 2 doses of 76 mg before further dose escalation. After dose escalation, if the 116 mg or 152 mg dose is not tolerated due to elranatamab-related grade 3 and higher toxicity, after consultation with the Sponsor, the participant may return to the 76 mg QW dosing regimen for 6 cycles followed by Q2W if PR or better is persisting for  $\geq 2$  months on QW.

For Part 1, if the RP2D (116 mg or 152 mg dose) Q4W is not tolerated after C7 and beyond due to elranatamab-related Grade 3 and higher toxicity, after consultation with the Sponsor, the participant may return to the 76 mg dose Q2W. Less frequent dosing may be required to manage adverse events.

If re-treatment criteria are not met within 4 weeks (8 weeks if participants are on Q4W or **PPD**) of treatment interruption/delay, study intervention should be permanently discontinued, unless the benefit/risk assessment per the investigator suggests otherwise, in agreement with the sponsor. In the event of a treatment interruption/delay lasting  $>4$  weeks ( $>8$  weeks if on Q4W **CCI**) for reasons other than treatment-related toxicity (eg, elective surgery), treatment resumption will be decided in consultation with the sponsor.

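### The return-to-76-mg rules in Protocol Section 6.5.1.2, read literally, allow re-treatment after toxicities for which Table 6 requires a permanent stop

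*Protocol*

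**What the plan says.** Two sentences in Protocol Section 6.5.1.2, placed after Table 6, deal with participants who cannot tolerate the higher doses.

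- **Part 2.** The trigger is "if the 116 mg or 152 mg dose is not tolerated due to elranatamab-related grade 3 and higher toxicity". After sponsor consultation the participant may go back to weekly 76 mg.
- **Part 1.** For a participant on 116 or 152 mg every four weeks from Cycle 7, the trigger and permission are "elranatamab-related Grade 3 and higher toxicity, after consultation with the Sponsor, the participant may return to the 76 mg dose Q2W".

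Table 6 in the same section contains these stops:

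- Non-hematologic toxicity, Grade 4: "Permanently discontinue". Footnote b narrows this: "Grade 3 or 4 nausea, vomiting or diarrhea must persist at Grade 3 or 4 despite maximal medical therapy" before a dose change or stop is required.
- Peripheral neuropathy, Grade 2 cell: "If Grade ≥2 neuropathy reoccurs, permanently discontinue elranatamab".
- Peripheral neuropathy, Grade 3 cell: withhold at the first occurrence, then "Recurrent: permanently discontinue elranatamab".
- Peripheral neuropathy, Grade 4 cell: permanent discontinuation.

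Two general statements point to the table. Section 6.5 says "In the event of significant toxicity, dosing may be modified in any cycle as described in" Table 6, and Section 6.5.1.2 opens with "The dose modifications for elranatamab-related toxicities and for peripheral neuropathy (any causality) are presented in" Table 6.

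**The concern.** The return sentences are open at the top of the grade scale, and their only stated condition is sponsor consultation. They therefore reach events for which Table 6 orders a permanent stop. An investigator facing such an event at 116 or 152 mg finds one provision that allows re-exposure at 76 mg and another that forbids it, with nothing to say which prevails.

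What is at stake is patient safety: re-exposure after a life-threatening related event or after recurrent severe neuropathy. The protocol treats peripheral neuropathy, including Guillain-Barré syndrome, as an important potential risk (Section 8.3.8.3). Parts 1, 2A and 2B were still ongoing at Amendment 4 (Section 4.1), so the wording was still in use then.

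**Working it through.** No arithmetic formula applies. The check compares what the return sentences cover with what Table 6 prescribes, and then looks for text that ranks the two.

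**Step 1: scope.** Both sentences cover elranatamab-related toxicity of Grade 3 or above. Table 6 has 3 toxicity rows × 4 grades = 12 cells, of which 3 × 2 = 6 are Grade 3 or 4. The Grade 3 neuropathy cell has two limbs, so there are seven categories to compare.

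| Related toxicity | Table 6 | Return sentences | Conflict |
|---|---|---|---|
| Non-hematologic, Grade 3 | Withhold, then resume | Return to 76 mg allowed | No |
| Non-hematologic, Grade 4 | Permanent stop, subject to footnote b | Return to 76 mg allowed | Yes |
| Hematologic, Grade 3 | Withhold, then resume | Return to 76 mg allowed | No |
| Hematologic, Grade 4 | Withhold until recovery | Return to 76 mg allowed | No |
| Neuropathy, Grade 3, first occurrence | Withhold until recovery | Return to 76 mg allowed | No, if there was no earlier Grade ≥2 episode |
| Neuropathy, Grade 3, recurrent | Permanent stop | Return to 76 mg allowed | Yes |
| Neuropathy, Grade 4 | Permanent stop | Return to 76 mg allowed | Yes |

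Three of the seven categories conflict. Counted by cell, 3 of the 6 Grade 3–4 cells contain a stop instruction. The Grade 2 neuropathy cell adds a fourth (4 of 12 overall): its recurrence rule also stops a Grade 3 event that follows an earlier Grade 2 episode. Grade 4 nausea, vomiting or diarrhea that does not persist falls outside the conflict because of footnote b.

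**Step 2: does any text rank the two rules?**

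- Sections 6.5 and 6.5.1.2 refer dose modification to Table 6 but do not say that it overrides the later, more specific return sentences.
- Section 6.5.1.1 sends re-treatment within a cycle to the tables and the accompanying guidance together, without ranking them.
- Section 4.3.3 allows dosing to resume after a dose-limiting toxicity only where that is permitted for the toxicity concerned. This covers dose-limiting toxicities in Parts 2A and 2C only, and it refers back to Section 6.5.1.2, which holds both rules. Part 1, Part 2B and events after the 28-day window are not covered.

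**Step 3: do the recovery criteria close the gap?** Section 6.5.1.1 requires treatment-related non-hematologic toxicity to return to baseline or Grade ≤1, and neuropathy to Grade ≤1, before a new cycle starts. That limits the risk. For the three conflicting categories, however, recovery is not the Table 6 test: the stop applies even after full recovery.

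**The case against.** The best defence is that the two provisions can be obeyed together. Table 6 is mandatory and the return sentences are permissive, so a permission can simply go unused where the table says stop. On this reading Table 6 decides whether treatment may resume, and the return sentences decide only the dose. The open-ended grade wording then has a proper use, because Grade 4 hematologic toxicity is a withhold rule and a capped trigger would wrongly remove the 76 mg option after, say, recovered Grade 4 neutropenia. Section 8 also bars protocol waivers. And where the authors wanted an exception to permanent discontinuation, they wrote one: the paragraph on prolonged interruption in Section 6.5.1.2 allows continuation on benefit/risk grounds with the sponsor's agreement.

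Much of this stands. The harmonized reading is probably what was intended, and the trigger should not be capped at Grade 3. But the reading is inferred, not stated. The bar on waivers does not settle it, because a return to 76 mg under these sentences is itself protocol text and needs no waiver. The exception for prolonged interruption cuts both ways: a site could infer from it that sponsor consultation can also lift a Table 6 stop.

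It is also fair to say that the cell counts describe the overlap in wording and do not measure risk. In practice, misuse would require a stop event at the higher dose, recovery, and both site and sponsor overlooking an explicit instruction in the same section. That limits the severity but does not remove the inconsistency.

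**Conclusion.** The concern holds as a minor point. Both return sentences literally permit re-treatment in three situations where Table 6 requires a permanent stop: related Grade 4 non-hematologic toxicity outside the footnote b exception, recurrent related Grade 3 neuropathy (including Grade 3 after an earlier Grade 2 episode), and related Grade 4 neuropathy. No text states that Table 6 prevails for Part 1, Part 2B or toxicity after the dose-limiting-toxicity window.

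The conclusion rests on the literal wording and does not assume that any site has acted on it. The number of participants exposed to the ambiguity cannot be estimated from the documents.

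**What to change.** Add a clause to both return-to-76-mg sentences in Section 6.5.1.2: *unless Table 6 requires permanent discontinuation*. Leave the Grade 3-and-above trigger as it is, so that the option remains for Grade 4 hematologic toxicity and for the footnote b cases.

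The cost is one clause in two sentences, by clarification letter or at the next amendment. Endpoints, sample size, visits, the SAP and planned outputs need no change. Any departure would already be covered by the protocol deviation summary in SAP Section 6.7.2.2.

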#### 4. STUDY DESIGN

##### 4.1. Overall Design

Study C1071009 is a prospective, open-label, multicenter, non-randomized Phase 1/2 study aimed to evaluate the safety (in particular the rate of Grade  $\geq 2$  CRS) of a priming dose regimen of eh-anatamab that involves premedication and 2 step-up priming doses to be administered within the first week of treatment (Part 1 and Part 2). Study C1071009 will include RRMM participants who are refractory to at least 1 PI, 1 IMiD, and 1 anti-CD38 mAb.

All participants enrolled in Part 1 and Part 2 will contribute to the primary objective of the study, ie, assessing the rate of Grade  $\geq 2$  CRS during C1, as the same dosing regimen is administered to all treatment groups during the first cycle.

Overall, at time of protocol amendment 4, Part 1 and Part 2 (Part 2A and Part 2B) were ongoing, and the enrollment is completed in all cohorts. Part 2C will not be explored. The RP2D was determined from Part 2A and is described below.

Twelve participants were enrolled and treated in Part 2A DL1 (116 mg Q2W from C2D1) and 7 were DLT evaluable. There was one DLT event. Eleven participants were enrolled and treated in Part 2A DL2 (152 mg Q2W from C2D1) and 7 were DLT evaluable. There was one DLT event. During the dose level review meeting (DLRM), the 152 mg Q2W dose was selected as the RP2D with a switch to 152 mg Q4W starting in Cycle 7 (for participants with an IMWG response of PR or better persisting for 2 months). In addition, participants in Part 1 dosed with 76 mg Q2W, with an IMWG response of PR or better persisting for 2 months were also permitted to switch to 152 mg Q4W. RP2D is currently investigated in Part 2B with a dosing of 152 mg Q2W or 152 mg Q4W (depending on IMWG response).

CCI  

All study parts are detailed below.

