## **Part 2: Premedication, 2 step-up priming doses, and full dose > 76 mg (ie 116 and 152 mg) at different dosing intervals**

Part 2 aims to evaluate the safety and efficacy of a regimen that includes premedication and a dosing regimen of 2 step-up priming doses (Week 1) followed by full dose >76 mg with different dosing intervals starting from C2.

Part 2 includes a dose determination (Part 2A Dose level 1 and Dose level 2), a dose expansion part (Part 2B), Part 2A dose determination and Part 2C tolerability evaluation will be based on a BLRM approach.

The decision to start enrolling participants in a new cohort (Part 2A Dose level 2, Part 2B or Part 2C) will be a joint decision to be determined by the investigators and the sponsor in dose level review meetings.

**Part 2A** will evaluate full ehanatamab doses >76 mg starting from C2 with a longer dosing interval (> 1 week) to determine the potential RP2D to be further evaluated in Part 2B. Approximately 8 participants will be enrolled at each dose level in Part 2A.

**Dose level 1** will assess the following regimen:

- **C2 to C6:** elranatamab 116 mg Q2W. DLT observation period is C2 or 28 days starting from the first dose of 116 mg. Hospitalization on C2 DI or on the day of the first dose of 116 mg for at least 1 day is required, see Section 2.3.1. Ehanatamab 116 mg represents an ~ 50% increase in ehanatamab dose versus 76 mg.
- **C7 onwards:** eh-anatamab 116 mg Q4W (for participants with IMWG response of PR or better persisting for 2 months on Q2W).

If Dose level 1 is tolerable, **Dose level 2** will be initiated to assess the following regimen:

- **C2 to C6:** ehanatamab 152 mg Q2W. DLT observation period is C2 or 28 days starting from the first dose of 152 mg. Hospitalization on C2 DI or on the day of the first dose of 152 mg for at least 1 day is required, see Section 2.3.1. Ehanatamab 152 mg represents an ~ 30% increase in ehanatamab dose versus 116 mg and will be the MAD in this study.
- **C7 onwards:** ehanatamab 152 mg Q4W (for participants with IMWG response of PR or better persisting for 2 months on Q2W).

- **CCI** [REDACTED]

The potential RP2D identified in Part 2A Dose level 1 or Dose level 2 will be further evaluated and confirmed in Part 2B (dose expansion).

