### 4.3.2. Justification for Evaluation of Higher Elranatamab Doses

An MTD was not achieved in C1071001, and the safety and efficacy for doses greater than 76 mg has not been established. Increasing the dose of elranatamab may allow for a longer dosing interval and a lower frequency of administration while maintaining the overall exposure (ie, AUC) of total eh-anatamab between 152 mg Q2W similar to 76 mg QW.

Based on the results of the quantitative systems pharmacology simulations, higher eh-anatamab doses with longer dosing intervals (ie, Q2W, Q4W and- are expected to be adequate to maintain the response given the reduced disease burden in these participants. The higher eh-anatamab dose levels explored in Part 2A/Part 2B, specifically Part 2A Dose level 2 of 152 mg Q2W/Q4W which is the target dose level for Part 2A/2B, provide a similar overall dose intensity (AUC) to 76 mg QW/Q2W. Dose level 1 (116 mg) represents ~ 50% increase from 76 mg. Dose level 2 (152 mg) represents ~ 30% increase from 116 mg. CCI

The dosing regimens to be evaluated in Part 2AIB, Part 2C and Part 1 after 6 cycles and after 12 cycles are expected to further saturate the sBCMA sink and result in higher unbound eh-anatamab exposure across the dosing interval. Therefore, these regimens could derive, maintain and/or further deepen clinical responses. In addition, less frequent dosing might provide additional patient convenience and improve compliance.

CCI

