6.7.3.1. Dose Reductions, Interruptions, and Delays

Dose Reduction

A dose reduction is defined as a non-zero dose that is less than the prior dose and less than the planned dose in the protocol.

The number and percentage of participants with at least 1 dose reduction as well as a breakdown of dose reductions (1/2/3/ ≥4) will be summarized. In addition, the number and percentage of participants with at least 1 dose reduction due to AE will also be summarized.

Dose Interruption

An interruption is defined as missing a scheduled dose based on the planned dosing frequency (QW, Q2W or Q4W).

The number and percentage of participants with dose interruptions as well as a breakdown of dose interruptions (1/2/3/ ≥4) will be summarized. In addition, the number and percentage of participants with at least 1 dose interruption due to AE will also be summarized. Percentages will be calculated based on the total number of participants in the Safety Analysis Set.

Dose Delay

A dose delay will be derived based on study drug administration date and will be grouped into the following categories based on the deviation of the actual to the planned treatment administration day (relative to the previous treatment administration date):

- No delay;
- 1-3 days delay;
- 4-6 days delay;
- 7 or more days delay (only in the Q2W and Q4W schedule).

The number and percentage of participants with delayed study drug administration and maximum length of delay, ie, the worst case of delay if participants have multiple dose delays will be summarized by cohort, as applicable.

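### For related Grade 3 or higher toxicity on 152 mg Q4W, Protocol 6.5.1.2 gives Part 1 and Part 2 different fallbacks, and the Part 2 one, as worded, doubles the weekly dose

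*Protocol*

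**What the plan says.** The text after Table 6 in Protocol Section 6.5.1.2 has one paragraph for each part.

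- **Part 2.** The trigger is "After dose escalation, if the 116 mg or 152 mg dose is not tolerated due to elranatamab-related grade 3 and higher toxicity". The fallback, open once the sponsor has been consulted, is that "the participant may return to the 76 mg QW dosing regimen for 6 cycles followed by Q2W", the later move to Q2W being conditional on a persisting response. Neither a dosing interval nor a cycle range is attached to the trigger.
- **Part 1.** The trigger is "if the RP2D (116 mg or 152 mg dose) Q4W is not tolerated after C7 and beyond due to elranatamab-related Grade 3 and higher toxicity". Once the sponsor has likewise been consulted, the rule is that "the participant may return to the 76 mg dose Q2W".

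Both parts use the 152 mg Q4W regimen. Section 4.1 gives, for Part 2A Dose level 2 from Cycle 7, "152 mg Q4W (for participants with IMWG response of PR or better persisting for 2 months on Q2W". It also says "RP2D is currently investigated in Part 2B with a dosing of 152 mg Q2W or 152 mg Q4W (depending on IMWG response". Part 1 responders on 76 mg Q2W were allowed to switch to 152 mg Q4W as well.

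On exposure, Section 4.3.2 says that the 152 mg Q2W/Q4W regimens "provide a similar overall dose intensity (AUC) to 76 mg QW/Q2W". That pairs 152 mg Q2W with 76 mg QW, and 152 mg Q4W with 76 mg Q2W. The risk table in Section 2.3.1 repeats the first pairing. Section 2.3.2 makes the same argument with 152 mg Q4W as its example.

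**The concern.** A participant on 152 mg Q4W who has a related Grade 3 or higher toxicity is handled differently according to study part, and the protocol gives no reason. The protocol's own equivalence makes the difference substantive. The Part 1 fallback is the regimen that Section 4.3.2 pairs with 152 mg Q4W. The Part 2 fallback is the regimen that it pairs with 152 mg Q2W, which has twice the dose intensity.

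At stake is a live instruction for use after severe drug-related toxicity. At Amendment 4 enrollment was complete, but Parts 1, 2A and 2B were all ongoing. An investigator and the sponsor's contact who consult Section 6.5.1.2 would start from different text depending on the part, and in Part 2 that text permits a higher weekly dose than the one that was not tolerated.

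**Working it through.** **Inputs.** Doses and intervals are from Protocol Sections 4.1 and 6.5.1.2. The measure is weekly dose = dose ÷ interval in weeks. This agrees with the planned cycle dose intensity in SAP Section 6.7.3 (planned mg in a 28-day cycle ÷ 4).

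**Step 1: reproduce the protocol's equivalence (Section 4.3.2).**

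- 152 mg Q2W: 152 ÷ 2 = 76 mg/week; 76 mg QW: 76 ÷ 1 = 76 mg/week.
- 152 mg Q4W: 152 ÷ 4 = 38 mg/week; 76 mg Q2W: 76 ÷ 2 = 38 mg/week.

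Both pairings reproduce exactly in mg/week.

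**Step 2: apply each fallback as written.**

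| Part | Regimen at toxicity | Before (mg/week) | Fallback | After (mg/week) | Ratio |
|---|---|---|---|---|---|
| 1 | 152 mg Q4W | 38 | 76 mg Q2W | 38 | 1.00 |
| 2 | 152 mg Q4W | 38 | 76 mg QW | 76 | 2.00 |
| 2 | 116 mg Q4W | 116 ÷ 4 = 29 | 76 mg QW | 76 | 2.62 |
| 2 | 116 mg Q2W | 116 ÷ 2 = 58 | 76 mg QW | 76 | 1.31 |
| 2 | 152 mg Q2W | 76 | 76 mg QW | 76 | 1.00 |

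The 116 mg rows concern Part 2A Dose level 1, where 12 participants were treated; 116 mg was not chosen as the RP2D.

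**Step 3: the six fallback cycles (24 weeks), starting from 152 mg Q4W.**

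- 76 mg QW: 76 × 24 = 1824 mg.
- 76 mg Q2W: 76 × 12 = 912 mg.
- 152 mg Q4W, had it continued: 152 × 6 = 912 mg.

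**Step 4: the single dose.** It falls in every case: 76 ÷ 152 = 0.50 and 76 ÷ 116 = 0.66. The rise is in weekly dose, the quantity behind the protocol's AUC argument.

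**Step 5: look for a limit on the Part 2 sentence.** No section confines it to the Q2W phase, and none explains why the parts differ on Q4W.

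**The case against.** The strongest reply is that the Part 2 sentence was meant for the step-up in Cycles 2 to 6. It directly follows the requirement for two 76 mg doses before escalation. The only 76 mg schedule that a Part 2 participant has already had is the weekly one in Cycle 1. The fallback also mirrors the Part 1 schedule, and from 152 mg Q2W it is neutral. This is a plausible account of the intent, and it stands as such. But the sentence has no such limit, and Part 2 participants do reach Q4W.

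A second reply also stands in part. Both fallbacks are permissive and need sponsor consultation. Table 6 withholds treatment for Grade 3 events until recovery and requires permanent discontinuation for Grade 4 non-hematologic toxicity. Section 6.5.1.3 makes dose delay the main tool. These provisions narrow the cases without removing the conflict. The remark ending the Part 1 paragraph, that dosing may need to be less frequent to manage adverse events, does not resolve it either.

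Stronger readings are tempting, but the documents do not support them:

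- **That the SAP would report the rise as a reduction.** SAP Section 6.7.3.1 begins "A dose reduction is defined as a non-zero dose that is less than the prior dose", but it adds a second condition: the dose must also be below the protocol's planned dose. Whether 76 mg becomes the planned dose after a fallback is not stated. In addition, SAP Section 6.7.3 summarizes dose intensity in mg/week and plots it by cycle over time, so a rise from 38 to 76 would show.
- **That peak exposure, and with it CRS risk, would rise.** The protocol ties CRS to Cmax after the first dose, and here each dose is smaller.
- **That a number of affected participants can be given.** The documents state neither how many reach Q4W nor how many then have a qualifying toxicity.
- **That tolerability of Q4W becomes uninterpretable.** The toxicity is recorded before any fallback, and SAP Section 5.2 reports the parts separately as well as combined.

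**Conclusion.** The concern holds as a contradiction within Section 6.5.1.2, and between its Part 2 paragraph and the dose-intensity reasoning in Sections 2.3.2 and 4.3.2. For the same toxicity on 152 mg Q4W, the Part 1 fallback leaves weekly dose unchanged (38 mg) and the Part 2 fallback permits 76 mg, a ratio of 2.0. From 116 mg Q4W the ratio is 2.6. Only from 152 mg Q2W is the Part 2 fallback neutral.

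The conclusion rests on two things: reading the Part 2 sentence as written, without an implied cycle limit, and using mg/week as the measure of dose intensity, as the SAP does and as the protocol's pairings imply. It does not show that any participant was or will be given a higher weekly dose, because the option is discretionary. Nor does it say which handling is correct. It warrants correction because the text governs management after severe drug-related toxicity in participants still on treatment.

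**What to change.** Reconcile the Part 1 and Part 2 paragraphs of Section 6.5.1.2 with each other and with Sections 2.3.2 and 4.3.2:

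- State whether the Part 2 sentence applies to participants already on Q4W or only to those on Q2W.
- For a regimen used in both parts, give one handling, or state the reason for the difference.
- Preferably list the fallback by regimen at toxicity onset (116 mg Q2W, 152 mg Q2W, 116 mg Q4W, 152 mg Q4W), with mg/week before and after beside each, so that the direction of change is visible.

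The regimens themselves are for the clinical team to decide. The cost is a few lines in an amendment or clarification letter, with no new data, visits or analyses.
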